Data from the Department of Veterans Affairs suggest that SCI affects an estimated 46,000 Veterans. With about 18,000 new cases of SCI every year, including a significant number of Veterans, the risk of osteoporosis and fracture is worth addressing. The first 2 weeks of SCI is the most critical for bone loss. Thereafter, progression slows down and stabilizes in 2-5 years and in some cases, far beyond 10 years. It is estimated that 50% -70% of individuals with SCI, will sustain a low impact fracture sometime in their lifetime. The sites commonly affected are the distal femur and proximal tibia. Osteoporosis-related fractures involve significant health care expenditure. The medical cost for managing Veterans with SCI alone in 2016 was estimated at \$30,770 - \$62,563 per Veteran, while cost in the acute phase could go above \$140,000^25. The cost of medical care for Veterans with SCI and osteoporosis-related fractures will naturally therefore, have significant impact on the finances of the VA healthcare system and those of Veterans and their families. It is estimated that health care cost for managing osteoporosis-related fractures, as a whole, will reach \$25 billion by 2025. Treating and preventing osteoporosis in persons with SCI is challenging. Anti-resorptive drugs (bisphosphonate and denosumab) and anabolics (PTH peptides), have been shown to reduce fracture risk at vertebral and hip sites. However, there is no consensus on whether they reduce fracture risk at the femur; the site of greatest relevance for persons with SCI. In contrast to anti-resorptive agents, sclerostin, which inhibits bone formation by up-regulating receptor activator of nuclear factor-kappa B ligand (RANKL) and down-regulating osteoprotegerin (OPG), with a net result of increased bone resorption, is emerging as a therapeutic target. Anti-sclerostin drugs (e.g. romosozumab), have been shown to stimulate bone formation, reduce resorption and ultimately increase BMD. Its use in the SCI population is however still being studied. It is only available in injectable form and has a black box warning for cardiovascular events/death, making it unattractive for use in a population already at high risk of cardiovascular events. Very importantly, electrical stimulation (ES) has been shown to partly reduce BMD loss in the femur if initiated early in SCI and it presents no systemic side effects. Bélanger et al., observed that the distal femur and proximal tibia had almost 30% recovery after 24 weeks of daily one-hour ES

treatment to the quadriceps muscles 5 days a week. However, there was no notable change in the mid-tibia. In another study of 24 persons with acute SCI receiving functional ES cycling exercises for 3 months, the rate of depletion in BMD in the distal femur, was significantly less in the study population compared to controls. We recently adopted neuromuscular electrical stimulation (NMES) resistant training (RT) to evoke muscular activity in paralyzed lower extremity muscles. Our preliminary data showed that just 16 weeks of **2 times a week** resulted in micro-architectural changes, suggesting that NMES-RT holds great promise as a therapeutic modality. We anticipate that a longer duration of treatment would yield even better outcomes. We therefore propose using telehealth to administer NMES-RT interventions over a 9-month period to improve the bone health of Veterans with SCI. Telehealth is an emerging utility that is gaining popularity. Using Telehealth for patient care has been shown to increase access and compliance. In a pilot study NMES-RT induced muscle hypertrophy by Gorgey et al., all participants were compliant with keeping their telehealth appointments and participation in the intervention activities. Additionally, vitamin D (Vit D) deficiency, defined as 25-hydroxyvitaminD 25(OH)D < 30ng/mL, has been implicated in decreased BMD, higher bone turnover, and higher incidence of bone fractures, whereas supplementation reduces fracture risk when major circulation 25(OH)D is sufficient.

Vit D depletion in persons with SCI was first observed in the early 90s, when Zhou et al., compared serum levels of 25(OH)D of 92 individuals with SCI (50 paraplegics and 42 quadriplegics) with those of 28 able-bodied persons. Serum 25(OH)D was low in SCI participants compared to the control group. Ultraviolet radiation from sunlight is the primary stimulant for the elaboration of Vit D. Deficiency can easily develop in SCI patients who have limited exposure to sunlight. Bauman et al. demonstrated that a sizable proportion of Veterans with chronic SCI have Vit D deficiency compared to non-SCIs in the general population. Although, Vit D deficiency is prevalent in the SCI population, the requisite amount of Vit D supplementation for correction of the deficiency has not yet been established. In a prospective drug intervention study, Bauman and Colleagues, used daily doses of 2000 IU of oral Vit D in Vit D deficient (< 20 mg/mL) subjects, plus 1.3 gram of elemental calcium to reach physiological levels of serum 25(OH)D, after 3 months. Another study used 6000 IU daily dose of Vit D in a double-blinded study, to achieve physiological range within the same time frame. The lower therapeutic dose in Bauman et al.'s study may be explained by the fact that Vit D is only needed for control of body calcium homeostasis, to improve calcium absorption for bone health. Lani et al. observed that calcium supplementation along with Vit D supplementation was necessary to achieve significant increase in bone mineralization in rat models. The authors suggested that even at higher doses, Vit D supplementation does not stimulate bone mineralization. Caution is however advised in the use of calcium supplementation in the SCI population, because of the risk of renal lithiasis and increased cardiovascular risks.

To our knowledge, no study has considered the combination of Vit D supplementation and NMES-RT for attenuation of bone loss after SCI. Prevention of osteoporosis and associated serious complications in the SCI population remains a major challenge and implementation of early interventions to mitigate complications and reduce health care cost is a worthwhile endeavor.

**Significance of this research to the Veterans' population:** The lack of weight bearing amongst Veterans with complete spinal cord injury and the prevalence of Vit. D deficiency, due to limited exposure to sunlight, is a significant problem. The consequence of these duo can result in low impact fracture leading to increased morbidity and mortality, as well as, high health care cost, increased care burden for the families and poor quality of life for the Veteran. The proposed study to use NMES-RT in conjunction with 2000 IU oral daily Vit D supplementation in Veterans with SCI of at least one-year post-injury, is a potential therapeutic strategy that may attenuate bone loss and decrease the frequency of low impact fractures after SCI. The fact that 50% of individuals with SCI will sustain low impact mechanical fractures during their lifetime, with an even higher incidence in Veterans, validates the need for this study. Additionally, the findings may help the VA healthcare system in the development of clinical guidelines for the prevention of osteoporosis in Veterans with SCI.

[figure not shown]
[figure not shown]
**Preliminary Study:** RT has been identified as a very important rehabilitation approach that increases lean mass and decreases fat mass. After SCI, RT has also been used to exercise both paralyzed and non-paralyzed muscles of lower extremities. NMES has been used in individuals with chronic SCI to evoke exercise-induced RT using standard ankle weights.

Fig 1

Mahoney et al. showed that **12 weeks of twice a week** NMES-RT resulted in skeletal muscle hypertrophy by more than 40% and improved glucose tolerance years after injury. A follow-up study reported that **fatigue resistance** of the trained knee extensors increased by 33%. Gorgey noted that **12-weeks of twice weekly** NMES-RT elicited more than 35% increase in skeletal muscle size, improved muscle quality, and increased insulin growth factor-1 (IGF-1) by 25%. The authors implemented 12 weeks of NMES-RT, 40 contractions per leg per session, in 9 individuals with motor complete SCI (C5-T11). Participants were randomly assigned into one of two groups; RT + diet (n=5; 4 tetraplegic)

[figure not shown]
or diet only (n=4; paraplegic). Skeletal Muscle Cross-Sectional Area (CSA) was measured with T1-axial MRI at **a) pre** and **b) post-12 week** of NMES-RT. Thigh (28%) and knee extensor muscle CSA (35%) showed remarkable hypertrophy (**Fig 2**). Another study demonstrated the effects of NMES-RT and Testosterone on cardio-metabolic risk factors after SCI. In an open-label randomized clinical trial, we examined the effects of complementary approach of 16 weeks of surface NMES evoked RT and testosterone (TRT+RT) compared to testosterone replacement therapy (TRT) only (2-6 mg) on skeletal muscle size, body composition, and peak torque (muscle quality) in persons with motor complete SCI. Twenty-two individuals with chronic motor complete SCI (ages 18-50 years) were randomly assigned to either TRT+RT (n =11) or TRT (n= 11) for 16 weeks (**Fig3**). In **fig. 3**, we determined the effects of TRT+ NMES-RT on whole thigh muscle CSA and whole thigh absolute muscle CSA after accounting for intramuscular fat. Compared to TRT only, TRT+ RT showed delta increase > 20 cm^2; demonstrating the efficacy of loading the paralyzed muscles in evoking muscle hypertrophy. Effects of NMES-RT with TRT on trabecular bone parameters of distal femur and proximal tibia were also measured. Nine participants with SCI were randomized into TRT+RT group for 16-week intervention. Each participant underwent MRI prior to BL and following the intervention PI. MRI microarchitecture techniques were used to evaluate trabecular bone quality, measured as plate width (PW;  $\mu$ m), trabecular bone thickness (TBTh; mm), trabecular bone spacing (TBSp; mm), and network area (NA; 1/mm) for the right proximal tibia (ProxT) and distal femur (DistF). Mixed models with random effects were used to calculate differences between BL and PI (MD  $\pm$  SE) and were then transformed to effect sizes similar to Cohen's d (d, 95% CI [effect size]). Bar plots for trabecular measures of the distal femur depicting the difference for each measure across the intervention period. Small effect sizes were observed for distal femur TBTh variability, TBSp, and NA. A medium effect size was observed for distal femur TBSp variability. Mean  $\pm$  SE. Bar plots for trabecular measures of the proximal tibia depicting the difference for each measure across the intervention period. A small effect size was observed for proximal tibia PW. Medium effect sizes were observed for ProxT, TBTh, TBSp, TBSp variability, and NA. Mean  $\pm$  SE. Following the intervention, ProxT PW (MD: 30.56  $\pm$  22.52; d: 0.48, -0.21 to 1.17 [small]), TBTh (MD: 0.02  $\pm$  0.01; d: 0.70, 0.01 to 1.39 [medium], and NA (MD: 0.04  $\pm$  0.02; d: 0.64, -0.05 to 1.33 [medium]) all increased from BL measures. In contrast, TBSp (MD: -0.25  $\pm$  0.17; d: -0.52, -1.22 to 0.17 [medium]) decreased from BL. The DistF similarly presented with increases in bone quality from BL for PW (MD: 11.7  $\pm$  42.70; d: 0.10, -0.60 to 0.79 [negligible]), TBTh (MD: 0.01  $\pm$  0.01; d: 0.29, -0.41 to 0.98 [negligible]), and NA (MD: 0.03  $\pm$  10/29/2019). **Fig. 4 & 5:** Due to the exploratory nature of the study on small sample size and short duration, we relied primarily in this trial on measuring the

effect size. Our results support the fact that the TRT+RT has a small effect size (<0.3) on parameters of trabecular bone at the distal femur and moderate effect size at proximal tibia (>0.5-0.8) compared to TRT only. Biostatistician advised that we should not run inferential statistics (**Holman et al. under review, Ost. Int.-R2**)

**Summary of preliminary data.** There are two key questions that are yet to be answered before deployment of this intervention; **1) Would NMES+RT +Vit D drive improvement in trabecular bone parameters compared to passive movement + Vit D in persons with chronic SCI? and 2) does skeletal muscle hypertrophy induce improvement in biomarkers of bone formation over bone resorption?** Our preliminary data is limited; however, it highlights the benefits of evoking skeletal muscle hypertrophy on trabecular bone parameters in persons with chronic SCI. We therefore posit that a home-based approach of 9 mos NMES-evoked RT and Vit D supplementation will enhance trabecular bone parameters and markers of bone formation compared to passive movement and Vit D supplementation.

Fig. 4

**Research Design and Methods:** A 2-year single site randomized controlled trial to investigate the efficacy of NMES-RT + Vit D versus passive movement + Vit D supplementation on trabecular bone parameters of distal femur and proximal tibia and on biomarkers of bone formation and resorption in persons with chronic SCI. All Recruitment will be conducted at CVHCS

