**Hypothesis: Osteoblastic and osteoclastic activities undergo obvious dynamic changes favoring bone loss after SCI.** NMES-RT +Vit D supplementation increases osteoblastic activity and decreases bone demineralization as observed by decreased biomarkers of osteoclastic activity compared to passive movement and Vit D supplementation.

**Subjects:** Twenty Veterans and non-Veterans with >1 year of SCI will be recruited from CVHCS and (VCU, if insufficient Veteran participants). The CVHCS SCI registry has ~1,800 Veterans and more than 298 meet the inclusion criteria of C8-T10 level of injury.

**Inclusion Criteria:** Participants should be 18-65 years of age; male or female, with traumatic motor complete SCI ( $\geq$ 1-year) and C8 to T10 neurological level of injury (NLI), by the International Standards for Neurological Classification (ISNCSCI) of SCI, serum 25(OH)D  $<$  41ng/mL, be a wheelchair user for primary mobility, be able to receive written clearance from their medical Providers to ensure safety of participants, accessible caregiver capable of physically supporting participant throughout the trial and willing to be trained to apply intervention protocol in the home (placing weights and positioning the Veteran) throughout study duration, and have normal ECG. Participants' knee extensors must respond to standard surface NMES procedures (frequency: 30 Hz; pulse duration:450  $\mu$ s and amplitude of the current  $<$  200 mA), to ensure intact neural circuitry below the level of SCI. All participants will undergo NLI examination. Only those with American Spinal Cord Injury Impairment Scale (AIS) **A and B** will be included. Age limit of 65 years is to avoid cardiovascular challenges that could be provoked by 9 months of strenuous physical activity in older persons. Moreover, persons older than 65, have more than 2-fold risk of osteoporosis related fractures, which may confound the trial.

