**Pitfalls and Alternatives:** Changes in trabecular bone parameters may be indeterminate because of the smallness and heterogeneity of sample size. We will rely on previous experience to calculate the effect size, and on that basis, adequately power future trials. **Failure to recruit proposed sample size:** The applicant's primary mentor ([name]) successfully conducted similar clinical trials in the past and demonstrated that use of telehealth facilitated recruitment and compliance among Veterans with SCI. Additionally, we may recruit non-Veterans to ensure completion of the study within the proposed timeline. [name] has a dual appointment with VCU and can successfully collaborate with VCU to ensure recruitment of the target sample size.

**Statistical Analyses.** After signing consent, the PI will randomly assign a number from 1-20 to participants using a computer program (nQuery). The order of enrollment will determine the participant's number based on level and duration of injury. Summary of information, including means and SD, frequencies and percentages, for all study variables will be calculated at all-time points. T-tests and Pearson chi-square tests will be used to compare characteristics that may act as confounders, including age, level and time since injury.

**Sample Size Justification:** Being a pilot study, consideration of sample size is just to allow determination and examination of preliminary evidence of efficacy and effect size estimation towards a larger future randomized trial. The proposed sample size of 10 per group is adjudged sufficient to accomplish these goals. Although Julious recommends a sample size of at least 12 per group on the basis that gain in precision for estimates of variance becomes relatively small on reaching a sample size of 12, we are unable to meet that target because of cost of the intervention and testing. Our sample size still allows for adequate accuracy. As shown in **Fig 6**, the gain in precision is still limited with a sample size of 10 per group. Although testing efficacy is not the primary goal, we will have 80% power to detect a standardized mean difference of  $d=0.9$  using an alpha of 0.25 corresponding to a large effect size. Type I error rates larger than 0.05 are often used and recommended for pilot studies where tests of efficacy are not the primary aim.

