**Data Analysis Plan:** IBM SPSS statistical software version 26 will be used. Being a pilot study, primary analyses will be mainly descriptive. Means and SD will be estimated for utilization (number of sessions completed), with each outcome. Finally, analysis of covariance (ANCOVA) will be used to test differences between groups post intervention for each outcome, using the baseline score as a covariate. If normality of groups appears to be violated in the sample normalizing transformations or non-parametric statistics will be considered.

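### Time since injury is named as a possible confounder and compared at baseline, but never enters the ANCOVA; with 10 per arm, a chance imbalance could distort the pilot's effect estimate

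*Combined protocol and SAP*

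**What the plan says.** - **Natural history.** Background and Rationale calls the first two weeks after injury the most critical for bone loss, then says that "progression slows down and stabilizes in 2-5 years and in some cases, far beyond 10 years".
- **Entry.** Under Subjects, "Twenty Veterans and non-Veterans with >1 year of SCI will be recruited". Both lists of inclusion criteria set a minimum of one year after injury. Neither sets a maximum.
- **Baseline comparison.** Statistical Analyses: "T-tests and Pearson chi-square tests will be used to compare characteristics that may act as confounders, including age, level and time since injury". Nothing is said about what follows if the arms differ.
- **Allocation.** The same paragraph says: "The order of enrollment will determine the participant's number based on level and duration of injury". It defines no strata, blocks or minimisation.
- **Outcome model.** Data Analysis Plan: "analysis of covariance (ANCOVA) will be used to test differences between groups post intervention for each outcome", "using the baseline score as a covariate". No other between-arm model and no sensitivity analysis is planned.
- **Size and purpose.** Sample Size Justification: "The proposed sample size of 10 per group is adjudged sufficient". The stated goals are preliminary evidence of efficacy and an effect size for a larger trial. The Data Analysis Plan describes the primary analyses as mainly descriptive.

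**The concern.** By the protocol's own account, some participants may still be losing bone at entry while others are stable. Their 9-month change could then differ without any treatment. The baseline score need not capture this: it measures how much bone is present, not how fast it is changing.

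The plan recognises the variable but stops at a baseline comparison. With 20 people, chance can leave one arm with more recently injured participants. If those are mainly controls, the training arm looks better than it should; if they are mainly in the training arm, a benefit is hidden. The main product of this pilot is an effect size, so an error here passes into the sizing of the next trial.

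**Working it through.** **Inputs from the documents:** 10 per arm; d = 0.9, alpha 0.25 and 80% power (Sample Size Justification); ANCOVA on the baseline score (Data Analysis Plan).

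**Assumptions:** simple randomisation; 4 to 10 of the 20 participants still in the losing phase; a correlation rho of 0 to 0.5 between time since injury and the outcome given baseline. The documents give neither of the last two figures.

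**1. The plan's power figure.** The noncentrality is 0.9 × √(10/2) = 2.012. The two-sided critical value at alpha 0.25 is 1.150. Power = Φ(2.012 − 1.150) = 80.6%. The noncentral t version with 18 df gives 79.6%. The stated 80% reproduces as a two-sided test; a one-sided test would give 91%.

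**2. How often the arms differ on a continuous scale.** The standardised mean difference in a baseline covariate has SD √(2/10) = 0.447. P(|difference| ≥ 0.5 SD) = 2 × [1 − Φ(0.5/0.447)] = 26%.

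**3. The same in counts.** Let K of the 20 be recently injured, and draw 10 per arm (hypergeometric). For K = 10, the probability that the counts differ by 4 or more is 2 × (120² + 45² + 10² + 1²)/184,756 = 2 × 16,526/184,756 = 17.9%.

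| K of 20 | Smallest split counted | Probability, either direction |
|---|---|---|
| 4 | 4 vs 0 | 8.7% |
| 6 | 5 vs 1 | 14.1% |
| 8 | 6 vs 2 | 17.0% |
| 10 | 7 vs 3 | 17.9% |

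An excess of 4 or more among controls specifically is half of each figure, about 4% to 9%.

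**4. What the baseline t-test detects.** With 18 df it is significant when the observed difference is at least t × 0.447. At 0.05 that is 2.101 × 0.447 = 0.94 SD. At 0.25 it is 1.189 × 0.447 = 0.53 SD. Under randomisation a test at 0.05 is significant in 5% of trials, so it flags about 5/26, or one in five, of the imbalances of 0.5 SD or more.

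**5. Error in the estimate when the imbalance is at least 0.5 SD.** The mean absolute imbalance in those trials is 0.447 × φ(1.118)/[1 − Φ(1.118)] ≈ 0.72 SD. Multiplying by rho gives 0.3 × 0.72 = 0.22 SD and 0.5 × 0.72 = 0.36 SD of the outcome given baseline. Against the design effect of 0.9 these are 24% and 40%.

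**6. Simulation.** 20,000 trials per row, normal data, baseline score independent of time since injury. Each cell shows ANCOVA on baseline only → ANCOVA with time since injury added.

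| rho | Mean error (SD), imbalance ≥ 0.5 SD | Type I error in those trials (nominal 25%) | Power at d = 0.9, all trials |
|---|---|---|---|
| 0 | 0.00 → 0.00 | 25% → 25% | 78% → 76% |
| 0.3 | 0.22 → 0.00 | 28% → 25% | 78% → 79% |
| 0.5 | 0.36 → 0.00 | 36% → 25% | 78% → 84% |

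Over all randomisations, type I error stays at about 25% under both models.

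**7. Precision.** The residual variance is multiplied by about (1 − rho²) × 17/16: 0.97 at rho = 0.3 and 0.80 at rho = 0.5.

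**The case against.** **The plan does not disregard time since injury.** A reader might infer that it does. It names the variable, compares it between arms, and mentions duration of injury in the allocation sentence. That stands: the gap is in the outcome model only. If the allocation sentence means stratification by duration, the probabilities in steps 2 and 3 do not apply. As written, it defines no strata.

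**Chance imbalance under randomisation is not systematic bias.** A reader might infer that the trial is confounded or has an inflated false-positive rate. Neither follows. Overall type I error is unchanged, and an imbalance can go either way. What remains is error conditional on the imbalance that actually occurs, plus some loss of precision.

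**The baseline test may be more sensitive than assumed.** The plan gives no alpha for it. At 0.25, the only alpha in the plan, it would flag differences from 0.53 SD. That stands, but no action follows from a significant result at either level.

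**Nothing shows that the effect is large.** This also stands. No correlation is given, and at rho = 0 the extra covariate costs a little power. A reader might also infer a clean split into losing and stable participants at five years. The protocol's own range, which extends in some cases far beyond 10 years, does not support such a cut.

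**It is a pilot, and age and level are named too.** Pilot status lowers the weight of the test but not of the estimate, which is a stated goal. Of the three named variables, age is limited to 18–65 and level to C8–T10. Time since injury alone has no upper limit, and it is the one whose time course of bone loss the protocol describes.

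**Conclusion.** The point holds as a gap in the outcome model: a variable that the protocol treats as potentially prognostic is tested at baseline, with no stated consequence, and left out of the ANCOVA. Under simple randomisation about one trial in four would have an imbalance of 0.5 SD or more. In those trials the estimate would be off by about 0.2 to 0.4 SD on average if the correlation is 0.3 to 0.5, and by nothing if it is zero. That correlation, the share of recently injured participants and simple randomisation are all assumptions. The documents do not support a claim of inflated overall type I error or of bias in a known direction. This is a cheap improvement to a pilot, worth making before data are seen.

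**What to change.** In the Data Analysis Plan, pre-specify time since injury (log years) as a covariate alongside the baseline score in the ANCOVA for the MRI, DXA and bone-marker outcomes, regardless of any baseline test. In Statistical Analyses, keep the baseline comparison as description only and state that its p-values will not decide adjustment. In the same paragraph, say what the allocation sentence means and whether duration of injury is a stratification factor.

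Optionally, plot each participant's 9-month change against time since injury by arm, as description only and without a fixed cut.

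The change is to wording: the plan already compares time since injury between arms, so the variable will be in hand. Residual degrees of freedom fall from 17 (20 − 3) to 16 (20 − 4). Power at d = 0.9 falls by about 2 points if the covariate is not prognostic, and rises by about 1 point at rho = 0.3 and 6 points at rho = 0.5. The sample size does not change.
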